2.4. Statistical Hypotheses

There is no formal research hypothesis that will be statistically tested in this study.

3. PLANNED ANALYSES

3.1. Final Analyses

The final planned primary analyses will be performed after the completion of the following sequential steps:

1. All participants have completed the study as defined in the protocol.
2. All required database cleaning activities have been completed and final database release (DBR) and database freeze (DBF) have been declared by Data Management.

The study early terminated due to potential contamination issue in study drug. All participants completed Treatment Period 2 before the study was terminated.

4. ANALYSIS POPULATIONS

Population	Definition / Criteria	Analyses Evaluated
Screened	
 All participants who signed the informed consent form This population will be used for screen failure listing and summary. 	
 Study Population
Randomized	
 All participants who were randomly assigned to a treatment sequence. This population will be used for listing of randomization schedule. 	
 Study Population
Safety	
 All participants who received at least 1 dose of study medication. This population will be used for all demographic, disposition (exclude screen failure), and safety listings, summaries, and figures 	
 Study Population Safety
Pharmacokinetic Concentration	
 All participants who underwent plasma PK sampling and had evaluable PK assay results. This population will be used for the PK concentration listings and summary tables. 	
 PK Concentration
Pharmacokinetic Parameter	
 All participants who underwent plasma PK sampling and had evaluable PK parameters estimated. This population will be used for PK parameter listings, summary tables, and statistical analysis tables. 	
 PK Parameter PK statistical analysis

Refer to [Appendix 9](#): List of Data Displays which details the population used for each display.

4.1. Protocol Deviations

Important protocol deviations (including deviations related to study inclusion/exclusion criteria, conduct of the trial, participant management or participant assessment) will be summarized and listed.

Protocol deviations will be tracked by the study team throughout the conduct of the study in accordance with the Protocol Deviation Management Plan. The “significant” protocol deviation in the Protocol Deviation Management Plan is equivalent to “important” protocol deviations.

CONFIDENTIAL

209713

- Data will be reviewed prior to freezing the database to ensure all significant deviations and deviations which may lead to exclusion from the analysis are captured and categorized on the protocol deviations dataset.
- This dataset will be the basis for the summaries and listings of protocol deviations.

A separate listing of all inclusion/exclusion criteria deviations will also be provided. This listing will be based on data as recorded on the inclusion/exclusion page of the electronic case report form (eCRF).

CONFIDENTIAL

209713

5. CONSIDERATIONS FOR DATA ANALYSES AND DATA HANDLING CONVENTIONS

5.1. Study Treatment & Sub-group Display Descriptors

Treatment Group Descriptions		
Data Displays for Reporting		
Description	Code	Order in TLF
GSK3640254 200 mg (single dose given as 2 × 100-mg capsules) administered under moderate fat condition	Treatment A	1
GSK3640254 200 mg (single dose given as 2 × 100-mg tablets) administered under moderate fat conditions	Treatment B	2
GSK3640254 200 mg (single dose given as 2 × 100-mg tablets) administered under fasted conditions	Treatment C	3
GSK3640254 200 mg (single dose given as 2 × 100-mg tablets) administered under high fat condition	Treatment D	4

5.2. Baseline Definitions

For vital signs and 12-lead ECGs, the baseline value will be the average (for quantitative assessments) or the worst case (for interpretation) of the triplicate predose assessments within each period. For clinical laboratory parameters, the baseline value will be the latest pre-dose assessment with a non-missing value, including those from unscheduled visits, before the first dose of study drug administration. If time is not collected, Day 1 assessments within each period are assumed to be taken prior to the dose and used as baseline.

Parameter	Study Assessments Considered as Baseline			Baseline Used in Data Display
	Screening	Day -1	Day 1 (Pre-Dose)	
Safety				
Vital Sign	X	X	X	Day 1 (Pre-Dose) ^[1] for each period
12-Lead ECG	X	X	X	Day 1 (Pre-Dose) ^[1] for each period
Hematology	X	X		Day -1
Clinical Chemistry	X	X		Day -1
Urinalysis	X	X		Day -1

ECG = Electrocardiogram.

[1] The average (for quantitative assessments) or the worst case (for interpretation) of the predose triplicate assessments will be used as the baseline.

Unless otherwise stated, if baseline data is missing no derivation will be performed and baseline will be set to missing.

CONFIDENTIAL

209713

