7.1.2. QTc Stopping Criteria

The *same* correction formula (QTcF) *must* be used for *each individual participant* to determine eligibility for and discontinuation from the study. This formula may not be changed or substituted once the participant has been enrolled.

- The Baseline QTcF should be based on averaged QTcF values of triplicate ECGs obtained over a brief (e.g., 5-10 minute) recording period from the Day -1 ECG.
- A randomized participant that develops an on-treatment QTcF >500 ms or an increase from Baseline QTcF >60 ms should have two repeat unscheduled ECGs within 10 minutes. Using these triplicate ECGs, if the average QTcF >500 ms or an increase from Baseline QTcF >60 ms, the participant will be withdrawn from the study. Finally, this participant should have repeated unscheduled ECGs until their QTcF measurement returns to their original averaged QTcF value at Day -1.

See the SoA (Section [1.3](#)) for data to be collected at the time of treatment discontinuation and follow-up and for any further evaluations that need to be completed.

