9. REFERENCES

ViiV Healthcare group of companies Document Number 2018N383392_00 (30-AUG-2019): A Randomized, Open-Label, Single Dose, Four-Period Crossover Clinical Trial to Assess the Relative Bioavailability of a Tablet Compared to a Capsule of GSK3640254 and to Assess the Effect of Food on the GSK3640254 Tablet in Healthy Participants.

CONFIDENTIAL

209713

10. APPENDICES**10.1. Appendix 1: Schedule of Activities****10.1.1. Protocol Defined Schedule of Events****Screening Visit**

Procedure	Screening (up to 28 days before Day 1)
Outpatient visit	X
Informed consent	X
Inclusion and exclusion criteria	X
Demography	X
Full physical examination including height and weight ¹	X
Laboratory assessments (hematology, chemistry, urinalysis)	X
12-lead electrocardiogram	X
Vital sign measurements	X
Medication/drug/alcohol history	X
Past and current medical conditions	X
Columbia Suicide Severity Rating Scale	X
Serum pregnancy test	X
Follicle-stimulating hormone (as needed, to confirm postmenopausal status)	X
Drug, alcohol, and cotinine screen	X
Human immunodeficiency virus, hepatitis B and C Screening	X

¹. A full physical examination will include at a minimum, assessments of the skin, cardiovascular, respiratory, gastrointestinal (GI), and neurological systems.

CONFIDENTIAL

209713

Time and Events Table

Procedure	Check-in	Periods 1, 2, and 3				Period 4 only				Notes	
		Day -1	Day 1	Washout			Day 1	Day 2	Days 3-4		Day 5 ⁰
				Day 2	Days 3-5	Days 6-7					
Admit to clinic	X										
Discharge from clinic									X	Discharge from clinic following completion of the last study procedure on Day 5 of Period 4.	
Brief physical examination	X				D7 (Period 2 only)				X	Interim or symptom targeted physical examination will be performed at the discretion of the investigator. See Protocol Section 8.2.1 for description of brief physical examination.	
Vital signs	X	X	X	D3-5		X	X	X	X	Blood pressure and pulse will be measured in triplicate predose on Day 1 in Periods 1-4. Single blood pressure and pulse will be measured predose on other study days.	
12-lead ECG	X	X				X			X	All ECGs on Day 1 in Periods 1-4 will be predose, postdose at 2 hours, and postdose at 4 hours. The predose ECGs in Periods 1-4 will be taken in triplicate.	
Drug, alcohol, and cotinine screen	X									See Protocol Appendix 2 for specific tests to be performed.	

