Laboratory assessments (hematology, chemistry, urinalysis)	X		X				X		X	See Protocol Appendix 2 for specific tests to be performed. Day 2 samples in each period to be collected 24 hours after dosing.	
Pregnancy test	X								X	Serum testing at Day -1	

CONFIDENTIAL

209713

Procedure	Check-in	Periods 1, 2, and 3				Period 4 only				Notes	
		Day -1	Day 1	Washout			Day 1	Day 2	Days 3-4		Day 5 ¹
				Day 2	Days 3-5	Days 6-7					
Columbia-Suicide Severity Rating Scale	X				D7				X		
Genetic sample (optional)	X										
Study intervention: GSK3640254 200 mg (capsule or tablet)		X				X				Participants will fast overnight for at least 10 hours prior to dosing; be provided a moderate fat meal, a high fat meal, or no meal 30 minutes prior to dosing; and be provided standardized meals ≥4 hours postdose. See Protocol Section 4.1.	
Serial PK sampling		X	X	X		X	X	X	X	Blood collection for PK analysis of GSK3640254 will be collected within 40 minutes prior to dosing and 1, 1.5, 2, 2.5, 3, 3.5, 4, 4.5, 5, 6, 8, 12, 24, 48, 72, and 96 hours postdose in each period.	
AE review		←-----X-----→									
SAE review		←-----X-----→									
Concomitant medications		←-----X-----→									

AE = adverse event; D = day; ECG = electrocardiogram; PK = pharmacokinetic; SAE = serious adverse event.

1 Evaluations scheduled for Day 5 in Period 4 will also be performed for participants who discontinue early.

CONFIDENTIAL

209713

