10.3.2. Reporting Standards

General

 The current GSK Integrated Data Standards Library (IDSL) will be applied for reporting, unless otherwise stated (IDSL Standards Location: https://spope.gsk.com/sites/IDSLLibrary/SitePages/Home.aspx): 
 4.03 to 4.23: General Principles 5.01 to 5.08: Principles Related to Data Listings 6.01 to 6.11: Principles Related to Summary Tables 7.01 to 7.13: Principles Related to Graphics Do not include participant level listings in the main body of the GSK CSR. All participant level listings should be located in the modular appendices as ICH or non-ICH listings.
Formats

 All data will be reported according to the actual treatment the participant received unless otherwise stated. GSK IDSL Statistical Principles (5.03 & 6.06.3) for decimal places (DP's) will be adopted for reporting of data based on the raw data collected, unless otherwise stated. Numeric data will be reported at the precision collected on the eCRF. The reported precision from non eCRF sources will follow the IDSL statistical principles but may be adjusted to a clinically interpretable number of DP's.
Planned and Actual Time

 Reporting for tables, figures, and formal statistical analyses: 
 Planned time relative to dosing will be used in figures, summaries, statistical analyses and calculation of any derived parameters, unless otherwise stated. The impact of any major deviation from the planned assessment times and/or scheduled visit days on the analyses and interpretation of the results will be assessed as appropriate. Reporting for Data Listings: 
 Planned and actual time relative to study drug dosing will be shown in listings (Refer to IDSL Statistical Principle 5.05.1).

CONFIDENTIAL

209713

 • Unscheduled or unplanned readings will be presented within the participant's listings. • Visits outside the protocol defined time-windows (i.e. recorded as protocol deviations) will be included in listings but omitted from figures (mean figures only for PK concentrations), summaries, and statistical analyses (excluding statistical analyses of PK parameters). 	
Unscheduled Visits	

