10.9.6. Safety Figures

Safety: Tables					
No.	Population	IDSL / Example Shell	Title	Programming Notes	Deliverable [Priority]
ECG					
2.1.	Safety	EG9	Mean (95% CI) Change from Baseline in QTcF Interval by Timepoint and Treatment		SAC

CONFIDENTIAL

209713

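### SAP 5.2 treats untimed Day 1 assessments as predose baseline with no exception for the 2 h and 4 h post-dose ECGs; the likely effect on the QTcF change displays is rare and small

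*SAP*

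**What the plan says.** SAP 5.2 defines the ECG and vital-sign baseline as the average "of the triplicate predose assessments within each period" (the worst case where the result is an interpretation). The table in 5.2 and its footnote repeat this. The laboratory baseline is different: the last non-missing value before the first dose, shown in the table as Day -1.

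A fallback for missing times follows: "If time is not collected, Day 1 assessments within each period are assumed to be taken prior to the dose and used as baseline". It names no parameter and no exception.

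The schedule, which is the same in Protocol 1.3 and SAP Appendix 1 (10.1.1), states "All ECGs on Day 1 in Periods 1-4 will be predose, postdose at 2 hours, and postdose at 4 hours" and "The predose ECGs in Periods 1-4 will be taken in triplicate". Each period therefore has five scheduled Day 1 tracings: three predose and two post-dose. Day 1 blood pressure and pulse are described only as predose triplicates. No laboratory draw is scheduled on Day 1; after Day -1 the next is on Day 2: "Day 2 samples in each period to be collected 24 hours after dosing".

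Two other provisions bear on the point. SAP 10.3.2 sets a general convention: "Planned time relative to dosing will be used in figures, summaries, statistical analyses and calculation of any derived parameters, unless otherwise stated". Protocol 7.1.2 says that a participant with a high QTcF reading "should have two repeat unscheduled ECGs within 10 minutes".

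**The concern.** The fallback refers to assessments within each period. Only ECGs and vital signs have per-period baselines, so these are what it chiefly governs. For scheduled vital signs the assumption is correct. For ECGs it is wrong for two of the five scheduled Day 1 tracings.

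If the rule were programmed as written, an untimed 2 h or 4 h ECG would do two things. It would be averaged into the value it should be compared with, and it would no longer count as a post-dose observation. When QTcF has risen, both effects understate the change.

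The protocol names QTc prolongation among the major risks (2.3). Median Tmax after a moderate fat breakfast was 3 to 4.5 h (2.2), so the 4 h tracing lies close to peak. The displays at stake are Table 2.12 (ECG changes from baseline) and Figure 2.1, titled "Mean (95% CI) Change from Baseline in QTcF Interval by Timepoint and Treatment".

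**Working it through.** The plan states no figure that depends on this rule, so there is none to reproduce. The size can be worked out from the schedule.

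**Formula.** Let k untimed post-dose tracings, each X ms above the true baseline, be averaged with the three predose tracings.

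- Baseline shift = kX/(3 + k).
- Change shown at a remaining post-dose time = X - kX/(3 + k).
- For k = 1: shift = X/4, change shown = 0.75X.

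**Plausible mean X after one dose.** These inputs come from Protocol 2.2.

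1. The predicted effects are 5.38 ms at 1779 ng/mL and 6.70 ms at 2154 ng/mL, so the implied slope is (6.70 - 5.38)/(2154 - 1779) = 1.32/375 = 0.00352 ms per ng/mL. The intercept is -0.9 ms.
2. Check: 0.00352 × 1779 - 0.9 = 5.36 ms, against the stated 5.38 ms.
3. Day 14 Cmax was 1.9 to 2.3 times Day 1 Cmax, so single-dose Cmax is about 1779/2.3 = 773 to 1779/1.9 = 936 ng/mL.
4. The effect is 0.00352 × 773 - 0.9 = 1.8 ms to 0.00352 × 936 - 0.9 = 2.4 ms.

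This assumes that the ratio range applies at 200 mg and that exposure resembles the earlier study. A different formulation or meal could change it, so the Day 14 prediction is added below as a higher illustration.

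**Result for k = 1, with equal X at 2 h and 4 h.**

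| True increase X (ms) | Baseline shift X/4 | Change shown, 0.75X |
|---|---|---|
| 1.8 | 0.5 | 1.4 |
| 2.4 | 0.6 | 1.8 |
| 5.38 | 1.345 | 4.035 |
| 65 | 16.25 | 48.75 |
| 80 | 20 | 60 |

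The threshold for a QTc increase in SAP 10.7.1 is above 60 msec. With one stray tracing the true increase must exceed 60/0.75 = 80 ms to cross it.

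**Effect on a treatment mean.** SAP 3.1 says that all participants completed Period 2 before termination. With the planned 16 participants, 4 per sequence (an assumption about actual numbers), each treatment was given in two sequences by then, so to 8 participants. One affected participant moves the mean at the remaining time point by X/(4 × 8) = X/32. That is 2.4/32 = 0.075 ms for X = 2.4 and 65/32 = 2.03 ms for X = 65. The other time point loses one participant.

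**Special case.** If the predose triplicate is missing, 5.2 would otherwise leave baseline missing. The literal fallback would make the untimed tracing the whole baseline, and all of X would be lost.

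**Which records are exposed.**

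| Day 1 ECG without a clock time | Planned time exists? | Position under the SAP |
|---|---|---|
| Predose triplicate | Yes | Fallback is correct |
| Scheduled 2 h or 4 h | Yes | 10.3.2 points to post-dose, the 5.2 fallback to predose; precedence not stated |
| Unscheduled | No | Only the fallback speaks to it, against the triplicate definition |

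**The case against.** The strongest defence is that the rest of the SAP already contains the right answer. SAP 5.2 gives the ECG baseline as the predose triplicate in text, table and footnote. SAP 10.3.2 uses planned time for derivations, and a scheduled 2 h or 4 h tracing has one. A sensible programmer would probably leave it post-dose. This largely stands. It is incomplete because 10.3.2 yields where something else is stated, 5.2 can be read as stating something else, and 5.2 does not say whether it means clock time or planned time.

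A second argument is that the fallback follows the laboratory sentence and may be meant for laboratory data. An unscheduled Day 1 sample could fall under it, but the per-period wording does not fit a single baseline taken before the first dose.

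A third is that nothing shows ECG times will be missing. Listings are to carry planned and actual time. This stands, and it makes the effect conditional.

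A reader might infer that a scheduled tracing and two triggered repeats, all untimed, could hide half of a 60 ms increase (3 × 60/6 = 30 ms). The documents do not support this as a realistic case. SAP 10.3.2 keeps unscheduled visits out of figures, and out of summary tables except for worst-case values. SAP 5.2 mentions unscheduled visits only for the laboratory baseline. All three times would also have to be missing.

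**Conclusion.** The fallback in SAP 5.2 is wrong as written for post-dose Day 1 ECGs, and the point is minor. It concerns only records without a time, and the documents do not show that any exist. Where it applied, one tracing would shift one participant-period's baseline by a quarter of the true increase: about 0.5 to 0.6 ms at the implied mean single-dose effect, more for an outlying individual. This assumes that the stray tracing is averaged with a complete predose triplicate and that the increase is similar at 2 h and 4 h.

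Three stronger readings are tempting and should not be drawn:

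- **An untimed post-dose QTcF simply becomes the baseline.** It would normally dilute a mean of three predose values; replacement needs the triplicate to be missing.
- **The error always hides harm.** It understates change when QTcF has risen. With an expected effect of about 2 ms, an individual post-dose reading can lie below baseline and shift it the other way.
- **Participant protection is weakened.** Protocol 7.1.2 uses a separate Day -1 triplicate baseline for stopping, which this rule does not touch.

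Only descriptive change displays are exposed. Absolute values remain visible in Listing 30, and Protocol 9.4.2 plans no formal analysis of safety data.

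**What to change.** Replace the fallback sentence in SAP 5.2 with wording to this effect:

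*Where the clock time of an assessment is missing, its planned time point governs. Only assessments planned as predose may be taken as predose and used for baseline. An ECG labelled 2 h or 4 h, and an unscheduled Day 1 ECG without a time, is never used as baseline.*

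This agrees with the predose-triplicate definition already in 5.2 and settles precedence with 10.3.2. It costs one sentence and one programming condition, and needs no new data. During the data review before database freeze (SAP 4.1), count the Day 1 ECG records without a time. If there are none, the change affects no result.

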5.3. Other Considerations for Data Analyses and Data Handling Conventions

Other considerations for data analyses and data handling conventions are outlined in the appendices:

Section	Component
10.1	Appendix 1: Schedule of Activities
10.2	Appendix 2: Study Phases and Treatment Emergent Adverse Events
10.3	Appendix 3: Data Display Standards & Handling Conventions
10.4	Appendix 4: Derived and Transformed Data
10.5	Appendix 5: Reporting Standards for Missing Data
10.6	Appendix 6: Division of AIDS (DAIDS) Table for Grading the Severity of Adult and Pediatric Adverse Events
10.7	Appendix 7: Values of Potential Clinical Importance

6. STUDY POPULATION ANALYSES

6.1. Overview of Planned Study Population Analyses

The study population analyses will be based on the Safety or Screened or Randomized population, unless otherwise specified.

Study population analyses including analyses of randomization schedule, participant disposition, protocol deviations (including inclusion/exclusion criteria deviations), demographic and baseline characteristics, prior and concomitant medications, and exposure will be based on GSK Core Data Standards. Details of the planned displays are presented in [Appendix 9](#): List of Data Displays.

7. PHARMACOKINETIC ANALYSES

7.1. Primary Pharmacokinetic Analyses

7.1.1. Endpoint / Variables

7.1.1.1. Drug Concentration Measures

Refer to [Appendix 3: Data Display Standards & Handling Conventions \(Section 10.3.3 Reporting Standards for Pharmacokinetics\)](#). Plasma concentrations of GSK3640254 will be measured and presented in tabular form and will be summarized descriptively. Plasma GSK3640254 concentration-time data will be listed by participant, treatment group and sampling time and summarized by treatment group and sampling time for each period of the study.

7.1.1.2. Derived Pharmacokinetic Parameters

Pharmacokinetic parameters will be calculated by standard non-compartmental analysis according to current working practices and using the currently supported version of WinNonlin (8.0 or higher). All calculations of non-compartmental parameters will be based on actual sampling times. Pharmacokinetic parameters listed will be determined from the plasma concentration-time data, as data permits. Subjects who experience emesis at or before 2 times median T_{max} will be excluded from the calculation of summary statistics and statistical analysis for the respective treatment.

Parameter	Parameter Description
AUC(0-∞)	Area under the plasma concentration-time curve from time 0 extrapolated to infinity, to be calculated using the linear trapezoidal rule for each incremental trapezoid and the log trapezoidal rule for each decremental trapezoid.
AUC(0-t)	Area under the plasma concentration-time curve from time 0 to the last quantifiable concentration, to be calculated using the linear trapezoidal rule for each incremental trapezoid and the log trapezoidal rule for each decremental trapezoid.
C _{max}	Maximum observed concentration, determined directly from the concentration-time data.
T _{max}	Time of maximum observed concentration

NOTES:

- Additional parameters may be included as required.

7.1.2. Summary Measure

Pharmacokinetic parameters AUC(0-∞), AUC(0-t), C_{max}, and T_{max} following single dose administration of GSK3640254 to healthy participants.

